7.2 Treatment Calendar

SCHEDULE OF EVENTS COHORT 1

Procedure	Screening (within 28 days prior to Day 0) ¹	Baseline Day 0	(C1D1)	Lead In C2 and C3	(C2 and 3D1) (± 3Days)	(C4+) (± 3 Days)	EOT	Follow Up ¹
Informed Consent	X							
Medical History	X							
Physical exam	X		X		X	X	X	
Vital Signs	X		X		X	X	X	
ECOG performance status	X		X		X	X	X	
Adverse Events	X		X		X	X	X	X
Concomitant Medications	X		X		X	X	X	X
CBCPD	X		X		X	X	X	
Comp	X		X		X	X	X	
Coagulation (PT/aPTT) ⁷	X							
FDG PET/CT-Chest (VA Ann Arbor) ²	X					X	X	
CT Abdomen/Pelvis ³	X							
Research Blood ⁴		X	X		X			
FLT PET (University of Michigan)		X	X					
Dexamethasone ⁵		X		X	X			
Pembrolizumab ⁶			X		X	X		

¹ Follow Up: Phone call 6 weeks after EOT including any new treatments

² FDG PET/CT-Chest: C4D1 (±7days), then Every 12 weeks (±7days)

³ CT-Abdomen/Pelvis: at screening, C4D1 (±7days), then Every 12 weeks (±7days) **only if disease is present in that area**

⁴ Research Blood: T/TK, SAP, cytokines, chemokines, immune cell subsets; Drawn with 1st FLT PET, 2nd FLT PET, C1D1, C2D1, C3D1 only

⁵ Dexamethasone given orally. Start immediately after FLT PET Day 0 – Day 9. Lead in Day 9-17

⁶ Pembrolizumab given up to 1 year every 21 days

⁷ Only required if clinically indicated or on anticoagulants

SCHEDULE OF EVENTS COHORT 2

Procedure	Screening (within 28 days prior to Day 0) ¹	Baseline Day 0	(C1D1)	Lead In C2 and C3	(C2 and 3D1) (± 3Days)	(C4+) (± 3 Days)	EOT	Follow Up ¹
Informed Consent	X							
Medical History	X							
Physical exam	X		X		X	X	X	
Vital Signs	X		X		X	X	X	
ECOG performance status	X		X		X	X	X	
Adverse Events	X		X		X	X	X	X
Concomitant Medications	X		X		X	X	X	X
CBCPD	X		X		X	X	X	
Comp	X		X		X	X	X	
Coagulation (PT/aPTT) ⁷	X							
FDG PET/CT-Chest (VA Ann Arbor) ²	X					X	X	
CT Abdomen/Pelvis ³	X							
Research Blood ⁴		X	X		X			
FLT PET (University of Michigan)		X	X					
Dexamethasone ⁵		X		X	X			
Pembrolizumab ⁶			X		X	X		

¹ Follow Up: Phone call 6 weeks after EOT including any new treatments

² FDG PET/CT-Chest: C4D1 (±7days), then Every 12 weeks (±7days)

³ CT-Abdomen/Pelvis: at screening, C4D1 (±7days), then Every 12 weeks (±7days) **only if disease is present in that area**

⁴Research Blood: T/TK, SAP, cytokines, chemokines, immune cell subsets; Drawn with 1st FLT PET, 2nd FLT PET, C1D1, C2D1, C3D1 only

⁵ Dexamethasone given orally. Start immediately after FLT PET Day 0 – Day 9. Lead in Day 9-17

⁶Pembrolizumab given up to 1 year every 21 days

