11.0 STATISTICAL ANALYSIS PLAN

11.1 Statistical Design (see page 10 for Schema)

In the first stage, three DEX escalation cohorts will be evaluated sequentially from Cohort A to Cohort C until two or more patients have the FLT-PET response (i.e., \geq 30% reduction in FLT-PET uptake in at least one target lesion) and, otherwise, the trial will be terminated due to futility. When a lead-in cohort has two or more FLT-PET responses, this lead-in cohort will be considered the optimal DEX duration and the primary endpoint will be evaluated in the following second and third stages using this optimal DEX duration. That is, after the optimal DEX duration is decided in the first stage, six additional patients will be enrolled in the second stage with the same DEX duration as the associated cohort. If four or less patients respond among 11 patients, the trial will be terminated. Otherwise, 10 additional patients will be enrolled in the third stage. The null hypothesis ($p_0 = 30\%$) will be rejected if 10 or more FLT-PET responses are observed in 21 patients. This design yields a 1-sided type I error rate of 5% and power of 80% when the true FLT-PET response rate is 60% (i.e., $p_1 = 60\%$). The minimum sample size will be 11 patients when Cohort A becomes the optimal duration and the trial is terminated at the end of the second stage. The maximum sample size will be 31 patients when Cohort C becomes the optimal duration and the patients are enrolled into the third stage.

We will also explore the associations between the FLT-PET response and the changes in senescence associated secretory proteins (SASP) and lymphocyte, phenotypic and functional markers (LPFM), (ii) monitor the changes and trajectories in SASP and LPFM, and (iii) explore the association between the FLT-PET response and GR expression at cycle 0. The expression levels of SASP and LPFM/GR will be measured using plasma and tissue samples,

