respectively. The secondary endpoints are the changes in SASP and LPFM expression levels between cycle 0 and cycle 1 as well as the expression level of GR at cycle 0. The association between the FLT-PET response and the changes in the expression levels of each of SASP and LPFM will be examined using logistic regression models. The expression levels of SASP and LPFM between cycle 0 and cycle 1 will be examined using a paired t-test, if needed, after data transformation (such as log or square root transformation). The association between the FLT-PET response and the GR expression level will be assessed using logistic regression models. The trajectories from cycle 0 to cycle 4 for the expression levels of each of SASP and LPFM will be examined to see if the expression levels increase monotonically across cycles. To do this, linear mixed-effects models will be used, if needed, after data transformation. In addition, in case that either Cohort B or C becomes the optimal duration, we will descriptively compare the changes in SASP and LPFM expression levels from cycle 0 to cycle 1 between lead-in cohorts. Because these are a discovery study to generate hypotheses, no multiple comparison correction will be made. However, if either the sample size is less than 12 patients or a level (i.e., response vs. non-response) has less than 5 events; all secondary objectives will be exploratory and will be summarized descriptively. All statistical analyses will be based on complete data and no missing data analysis will be performed.

The secondary objective is to assess the effect of DEX on pembrolizumab in terms of overall response rate (ORR), which is the primary endpoint. Based on our previous pre-clinical and clinical studies, we hypothesize that the true ORR of DEX followed by pembrolizumab will be at least 33% (i.e., $p_1 = 0.33$) vs. the historical control whose ORR is at most 7% (i.e., $p_0 = 0.07$). The ORR will be statistically evaluated when the FLT-PET response trial enters the third stage, where the number of patients with the selected optimal DEX duration will be 21. Otherwise, the ORR will be summarized descriptively. The null hypothesis ($p_0 = 7\%$) will be rejected if five or more responses are observed in 21 patients, which yields a 1-sided type I error rate of 5% and power of 87% when the true ORR is 33% (i.e., $p_1 = 33\%$).

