11.2 Sample Size Justification

The clinical trial is a single arm phase II intervention trial in Veterans as second line therapy, after progression on initial chemo-immunotherapy or immunotherapy for NSCLC. The enrolled patient will be in the study for 3 months and will then be followed for up to 2 years. We currently see at least 2-3 patients per month who will satisfy eligibility criteria and thus

the enrollment will be completed within 2 years (min 21 and max 39 patients). A sample size of 21 patients will not be powered for all the comparisons. But the data information obtained from this study will provide us preliminary information to design a more definitive study

The sample size was justified based on the primary objective. The FLT-PET response will be evaluated using a Phase II single-arm three-stage design with three lead-in efficacy (futility) cohorts. The sample size was estimated to achieve 80% power with a 1-sided 5% type I error rate and the estimated sample size is varied according to the selected optimal duration, which ranges from 21 patients (when Cohort A is optimal) to 31 patients (when Cohort C is optimal). Considering up to 20% drop-out rate, the required sample size will be between 21 patients (i.e., no drop-out with Cohort A as the optimal duration) and 39 patients (i.e., 20% drop-out with Cohort C as the optimal duration). For the secondary objective, the use of 21 patients (when the FLT-PET response trial enters the third stage) will allow us to achieve 87% power when the true ORR is 33% with a 1-sided type I error rate of 5%. We expect that the accrual rate will be at least 35 eligible and evaluable patients per year.

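### Read literally, the complete-data rule drops partial marker series from the mixed models and can bias the SASP and LPFM slopes if loss is marker-related

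*Combined protocol and SAP*

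**What the plan says.** Section 11.1 sets a repeated-measures aim: "The trajectories from cycle 0 to cycle 4 for the expression levels of each of SASP and LPFM will be examined", with the question being whether levels rise steadily over cycles. The method follows: "To do this, linear mixed-effects models will be used, if needed, after data transformation". The same paragraph ends with the rule "All statistical analyses will be based on complete data and no missing data analysis will be performed". The identical sentence closes the later paragraph on associations with ORR and on PFS. Neither place exempts the mixed models or says what counts as complete.

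The calendar in Section 7.2 limits research blood as follows: "Drawn with 1st FLT PET, 2nd FLT PET, C1D1, C2D1, C3D1 only". In the Appendix IV diaries the second FLT-PET and C1D1 fall on the same day, so there are four draw days: day 0, C1D1, C2D1 and C3D1. No cycle 4 draw is scheduled. The first on-treatment response scan comes after the last draw: "FDG PET/CT-Chest: C4D1 (±7days), then Every 12 weeks (±7days".

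The only drop-out figure is in Section 11.2: "Considering up to 20% drop-out rate, the required sample size will be between 21 patients" and 39. Section 11.1 calls the marker work hypothesis-generating and makes it descriptive below 12 patients, or when responders or non-responders number fewer than 5.

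**The concern.** A likelihood-based mixed model accepts unequal numbers of draws per patient and needs no imputation. Under missing at random (loss depends only on values already observed), it estimates the mean slope of the whole group from whatever was drawn. A rule requiring full series removes that property: the day 0, C1D1 and C2D1 samples of a patient who stops before C3D1 are set aside, and the slope then describes only patients who stayed to the last draw.

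Some early loss is foreseeable. Counting diary rows, C3D1 falls 54 days after the first dexamethasone dose in Cohort 1 (12 lead-in days plus 42) and 76 days after it in Cohort 3 (20 plus 56). Section 4.2.1 describes survival in this setting as often under six months. Section 8.0 says unstable clinical progressors should not continue on therapy.

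If patients who leave early are those whose markers rose least, the complete-case slope is too steep, which is the direction the analysis looks for. Section 11.2 intends these data to inform a larger study, so a rise that is partly selection could be carried forward.

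**Working it through.** **1. The plan's own figure.** Section 11.1 says "The maximum sample size will be 31 patients when Cohort C becomes the optimal duration". Inflating for 20% loss: 31 / (1 − 0.20) = 38.75, rounded up to 39, as Section 11.2 states. No stated figure is wrong on this point. The documents give no figure for marker variance, marker slope or loss before C3D1, so the rest is an illustration.

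**2. Samples at stake.** At n = 21 and 20% loss, 21 × 0.80 = 16.8, so about 17 patients have full series and about 4 do not. If those 4 each gave three of the four draws, 17 × 4 + 4 × 3 = 80 samples exist, and the literal rule discards 12 of them.

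**3. Assumptions for the slope.** Four draws at t = 0, 1, 2, 3; between-patient SD 1; mean slope 0.20 SD per cycle; slope SD 0.30; residual SD 0.50. The plan's overall 20% drop-out stands in for loss before the last draw, with 10% and 30% shown as a range.

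**4. Sharp cut-off, closed form.** Suppose the patients with the lowest observed change from t = 0 to t = 2 miss the last draw.
- SD of that change: √(4 × 0.09 + 2 × 0.25) = √0.86 = 0.927.
- Covariance of a completer's fitted slope with that change (regression weights −0.3, −0.1, 0.1, 0.3): 2 × 0.09 + 0.25 × (0.1 + 0.3) = 0.28.
- Bias = λ × 0.28 / 0.927, where λ is the standard normal density at the cut-off divided by the proportion kept.
- 20% loss: λ = 0.280 / 0.80 = 0.350; bias = 0.106; complete-case slope 0.31.
- 10% loss: λ = 0.195; slope 0.26. 30% loss: λ = 0.497; slope 0.35.

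A simulation of the same rule gives 0.26, 0.31 and 0.35 for completers, and 0.20 each time when all draws are used.

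**5. Probabilistic loss.** Patients may stop after the cycle 1 or cycle 2 draw. The log-odds of stopping change by 1 to 2 per SD, either of the observed marker change or of the patient's own unobserved slope. There were 300,000 simulated patients per scenario, and the slope was fitted by generalised least squares with known covariance.

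| Loss depends on | Analysis | 10% | 20% | 30% |
|---|---|---|---|---|
| Nothing related to the marker | Completers | 0.20 | 0.20 | 0.20 |
| | All draws | 0.20 | 0.20 | 0.20 |
| Observed change | Completers | 0.22–0.23 | 0.24–0.26 | 0.26–0.29 |
| | All draws | 0.20 | 0.20 | 0.20 |
| Unobserved slope | Completers | 0.23–0.24 | 0.25–0.28 | 0.28–0.32 |
| | All draws | 0.22–0.23 | 0.23–0.25 | 0.24–0.27 |

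Combining steps 4 and 5, at 20% loss the complete-case slope is 0.20 with unrelated loss and about 0.24 to 0.31 when loss depends on observed change.

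**6. Window against schedule.** Section 11.1 names cycles 0 to 4, whereas Section 7.2 stops research blood at C3D1. Section 11.4 speaks of later time points at cycles 2 and 3, which fits the calendar and not Section 11.1. If complete meant a full cycle 0 to 4 series, no patient would qualify from scheduled draws.

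**The case against.** The strongest reply is that deletion is inferred. Complete data with no missing-data analysis can also mean observed data without imputation. The choice of a mixed model in the same paragraph fits that reading, under which nothing is lost. This stands as a fair alternative. It does not remove the point: two analysts could follow the text and report different slopes from the same samples.

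Four further limits stand.
- Bias needs a link between loss and the marker; without one it is zero.
- The direction need not be the same for every marker. The panel in Section 4.2.3 covers 45 analytes including IL-6 and VEGF, and Section 4.1 associates dexamethasone's tumour inhibition with down-regulation of both.
- The last draw precedes the first response scan, treatment beyond progression is allowed, and entry requires six months' life expectancy. Loss before C3D1 would therefore come mainly from toxicity, clinical deterioration, death or withdrawal, and may be below 20%.
- The trajectory is not among the marker endpoints that Section 11.1 names (changes from cycle 0 to cycle 1, and baseline GR), and no decision rule uses it.

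A reader might infer that the plan certainly discards early leavers, that these are the non-responders, and that the reported rise will be inflated to something like 0.35 against a true 0.20. The documents do not support that. They do not define complete data, do not show who will leave before C3D1, and give no source for 30% loss; 0.35 also needs a sharp cut-off and the particular SDs assumed here.

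**Conclusion.** The point holds in conditional form. As worded, the rule covers the mixed models, and its literal reading gives up partial series for no gain. At the plan's 20% drop-out and under the assumed values, the resulting bias runs from none to about 0.11 on a true slope of 0.20, depending on how loss relates to the marker. Using all observed draws removes the bias when loss depends on observed values and reduces it when loss depends on unobserved ones. It was never worse than the complete-case analysis in the scenarios run.

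The sizes rest on assumed variances, four draws, and an overall drop-out figure used in place of loss before C3D1. The consequence is confined to a hypothesis-generating analysis; the primary FLT-PET test and the ORR test do not depend on it. The mismatch between the cycle 0 to 4 window and the draw schedule is a separate inconsistency that needs no assumptions.

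**What to change.** For these models, replace the complete-data rule in Section 11.1 with:

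*Linear mixed-effects models will use all observed samples from every patient in the analysis population, by likelihood, without imputation; the complete-data restriction does not apply to them.*

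Name which Section 11.3 population is meant. State that the analysis assumes missing at random, and report the number of samples available at each draw with reasons for stopping. A short comparison of completers with non-completers would show how far that assumption matters.

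Reconcile the trajectory window in Section 11.1 with the draw schedule in Section 7.2, so that the cycles analysed are cycles at which blood is drawn.

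The cost is a sentence and a small table. No extra patients are needed, and no extra samples if the window is matched to the existing draws. If the sponsor already meant all observed draws, the change only makes that explicit.

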11.2 Sample Size Justification

The clinical trial is a single arm phase II intervention trial in Veterans as second line therapy, after progression on initial chemo-immunotherapy or immunotherapy for NSCLC. The enrolled patient will be in the study for 3 months and will then be followed for up to 2 years. We currently see at least 2-3 patients per month who will satisfy eligibility criteria and thus

the enrollment will be completed within 2 years (min 21 and max 39 patients). A sample size of 21 patients will not be powered for all the comparisons. But the data information obtained from this study will provide us preliminary information to design a more definitive study

The sample size was justified based on the primary objective. The FLT-PET response will be evaluated using a Phase II single-arm three-stage design with three lead-in efficacy (futility) cohorts. The sample size was estimated to achieve 80% power with a 1-sided 5% type I error rate and the estimated sample size is varied according to the selected optimal duration, which ranges from 21 patients (when Cohort A is optimal) to 31 patients (when Cohort C is optimal). Considering up to 20% drop-out rate, the required sample size will be between 21 patients (i.e., no drop-out with Cohort A as the optimal duration) and 39 patients (i.e., 20% drop-out with Cohort C as the optimal duration). For the secondary objective, the use of 21 patients (when the FLT-PET response trial enters the third stage) will allow us to achieve 87% power when the true ORR is 33% with a 1-sided type I error rate of 5%. We expect that the accrual rate will be at least 35 eligible and evaluable patients per year.

11.3 Population for Analysis

Intent-to-Treat Population: All patients consented and enrolled in the trial.

Evaluable Population: Only those patients who have received at least one cycle of therapy with dexamethasone and pembrolizumab will be considered evaluable.

Safety Evaluable Population: Patients who receive any treatment on protocol will be considered evaluable for safety.

11.4 Analysis of Primary Objective: The primary objective is to identify the smallest duration of fixed dose Dex that results in a >30% reduction in FLTPET. We will utilize a 2 stage design with 3 cohorts (see Statistical schema). The hypothesis is that the true “response” in FLTPET (reduction in FLTPET by >30% following Dex in at least 1 target lesion) will be 60% ($p_1=60$) vs. p_0 30% (based on preliminary data that chemotherapy such as docetaxel results in irreversible cell cycle arrest as measured by S-phase surrogate on FLT-PET (39)).

Secondarily, we will compare FLTPET “response” to GR expression and generation of SASP and immune effector cells. We will also track the trend in immune effector cell response at later time points (cycle 2 and 3) to test contributory effects of pembrolizumab and Dex on the immune phenotype in the blood.

11.5 Analysis of Secondary Objectives The secondary objective is to establish that the true ORR of Dex followed by pembrolizumab will be at least 33% ($p_1 = 0.33$) vs. docetaxel treatment (as the historical control) whose ORR is

$\leq 7\%$ ($p_0 = 0.07$). The ORR will be assessed at a 12 week FDG PET scan. The required sample size for both lead-in FLTPET response and phase 2 studies will range 21 to 31 patients. As secondary objectives, we will explore associations of the change in FLT-PET with ORR assessed by FDG-PET, level of plasma SASP, and immune cell activation. The change in FLT-PET will be compared by ORR using an unpaired t-test and the associations with the level of plasma SASP and immune cell activation will be examined by a correlation analysis. The power is not formally justified because these are exploratory

12.0 LABELING, PACKAGING, STORAGE AND RETURN OF CLINICAL SUPPLIES

12.1 Investigational Drugs

The investigator shall take responsibility for and shall take all steps to maintain appropriate records and ensure appropriate supply, storage, handling, distribution and usage of study drug in accordance with the protocol and any applicable laws and regulations.

Dexamethasone is available through commercial supply. It will be administered orally according to study schema.

Pembrolizumab is available through commercial supply. It will be administered intravenously every 21 days per institutional standard policy

Product Name & Potency	Dosage Form
Pembrolizumab 50 mg	Lyophilized Powder for Injection
Pembrolizumab 100 mg/ 4mL	Solution for Injection

Dexamethasone is available through commercial supply and will be administered 7 days prior with 3 days off before each pembrolizumab infusion.

Drug Name:	Dexamethasone
INN:	Dexamethasone
Formulation:	Tablet;

How Supplied:	2mg white, scored tablet 4mg green, scored tablet 6 mg aqua, scored tablet Come in high-density polyethylene bottles or equivalent with child-resistant caps. Patients may receive 1 or more strengths. Each bottle contains 100 tablets
Storage Conditions:	20-25 °C (68 and 77° F) protect from moisture

12.2 Clinical Supplies Disclosure

This trial is open-label; therefore, the subject, the and trial site personnel are not blinded to treatment. Drug identity (name, strength) is included in the label text.

12.3 Storage and Handling Requirements

Clinical supplies must be stored in a secure, limited-access location under the storage conditions specified on the label.

Clinical supplies may not be used for any purpose other than that stated in the protocol.

13.0 ADMINISTRATIVE AND REGULATORY DETAILS

13.1 Compliance with Trial Registration and Results Posting Requirements

Under the terms of the Food and Drug Administration Modernization Act (FDAMA) and the Food and Drug Administration Amendments Act (FDAAA), the PI of the trial is solely responsible for determining whether the trial and its results are subject to the requirements for submission to the Clinical Trials Data Bank, <http://www.clinicaltrials.gov>. Information posted will allow subjects to identify potentially appropriate trials for their disease conditions and pursue participation by calling a central contact number for further information on appropriate trial locations and trial site contact information.

13.2 Quality Management System

The Ann Arbor VA Research Office audits clinical trials every quarter and random charts are examined for any discrepancies as relates to HIPPA adherence and IRB approved form usage

